Specific Aim 1. To assess the efficacy of pain coping skills training in reducing knee pain and improving function. Our two primary hypotheses (to be tested in the clinical trial) are the following:

- **Hypothesis 1a.** Pain coping skills training is more effective than arthritis care education in *decreasing knee pain during functional activities*.
- **Hypothesis 1b.** Pain coping skills training is more effective than usual care in *decreasing knee pain during functional activities*.

We also will examine **one secondary (hyp. 2) and one tertiary (hyp. 3) hypothesis**.

- **Hypothesis 2.** Pain coping skills training is more effective than arthritis education or usual care in improving self-reported function, physical performance, pain intensity, pain catastrophizing, and patient global ratings of improvement.
- **Hypothesis 3.** Pain coping skills training will reduce direct medical costs and indirect (i.e. patient time) costs relative to arthritis care education and usual care. When accounting for costs associated with pain coping skills training, the intervention will be cost saving or cost-effective relative to arthritis care education and usual care as measured by the incremental cost per quality-adjusted life-year.

Specific Aim 2. To determine if treatment benefits of pain coping skills are mediated by changes in pain catastrophizing:

- **Hypothesis 4.** Changes in pain catastrophizing that occur over the course of pain coping skills training will mediate treatment-related improvements in pain and self-reported function during recovery.
-

Research Strategy

Significance: Specific Aim 1

Knee arthroplasty surgery (TKA) is a common and generally effective procedure.¹ For example, projections estimate that 3.5 million procedures will be conducted annually by 2030.² Cost data for TKA also are impressive. Mean procedural charges per patient in 2003, reported in 2005 dollars, were \$38,000 per primary surgery and \$48,000 per revision surgery.³ If these procedural charges data were extrapolated to the 2010 volume data projections, procedural charges would total approximately \$28 billion dollars annually.

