The incremental cost effectiveness ratio (ICER) will be calculated as the difference in the mean cost per patient between study arms divided by the difference in estimated quality-adjusted life-years (QALYs). Mean costs will be estimated as described above. Quality-adjusted life-years will be estimated using utility estimates derived from the EQ-5D. Because the interventions represent fixed-, one-time costs while the benefits of the interventions may last beyond the one year follow-up period in the KASTpain study, we will conduct sensitivity analyses that extrapolate differences in utilities measured at the end of follow-up over 3, 5, and 10 years, assuming that the interventions do not differentially impact survival. If we observe statistically significant differences in costs (not including intervention costs) between treatment arms at 12 months, we will extrapolate treatment-specific cost estimates over 3, 5, and 10 years, consistent with the time period for QALYs. We will evaluate uncertainty by estimating 95% CIs for estimates of costs, QALYs and measures of cost-effectiveness (i.e. ICERs or net health benefits¹⁴³) using nonparametric bootstrapping.^{141,142}

Timetable and Milestone Plan

The milestone plan is as follows:

Enrollment of the first subject: Prior to enrolling the first subject, all sites will be required to complete IRB approval procedures and interview, hire and train research staff including the clinical psychologists and nurse educators. All study staff will be required to complete training in the study protocol as described in the MOOP and will also require time to develop working relationships with orthopaedic surgery staff in preparation for patient recruitment and retention. Clinical psychologist training will require travel to Duke University while the PI will travel to each site to train the nurse educators. We expect to have all IRB, hiring and training procedures

completed and should be fully prepared to begin study recruitment within 6 months of the beginning of the study. Assuming that the study will begin on April 1, 2012, the first subject will be recruited by October 1, 2012.

[figure not shown]
25%, 50%, 75% and 100% enrollment projections: We expect enrollment for these various thresholds to occur by the following time periods listed on Table 4 below. The recruitment period will require, at maximum, a total of 3 years.

Table 4 Summary of Recruitment Goals

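### Hypothesis 3 has no lead cost-effectiveness measure and no cost-per-QALY threshold, and the bootstrap 95% CI allowed for the ICER breaks down when the QALY difference may be zero

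*Combined protocol and SAP*

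**What the plan says.** Hypothesis 3 (Specific Aims), labelled tertiary, has two parts. The first concerns costs alone: "Pain coping skills training will reduce direct medical costs and indirect (i.e. patient time) costs relative to arthritis care education and usual care". The second counts the cost of the intervention and predicts that "the intervention will be cost saving or cost-effective relative to arthritis care education and usual care", "as measured by the incremental cost per quality-adjusted life-year".

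The Cost Analysis section compares mean total costs over one year, and the medical and indirect components, directly between arms.

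The Cost-Effectiveness Analysis section says the ICER "will be calculated as the difference in the mean cost per patient between study arms divided by the difference in estimated quality-adjusted life-years". Uncertainty is covered in one sentence: "We will evaluate uncertainty by estimating 95% CIs for estimates of costs, QALYs and measures of cost-effectiveness (i.e. ICERs or net health benefits", with the intervals obtained "using nonparametric bootstrapping". The two cost-effectiveness measures are offered as alternatives.

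The document gives no willingness-to-pay value or range, no rule for choosing between the measures, no cost-effectiveness plane or acceptability curve, and no criterion for calling the second part of Hypothesis 3 supported.

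**The concern.** The ICER is a ratio whose denominator can be zero or negative, which causes two problems.

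- **Sign.** Cheaper-and-better and dearer-and-worse both give a negative ratio. Dearer-and-better and cheaper-and-worse both give a positive one. The number means something only alongside its quadrant.
- **Order.** As the QALY difference passes through zero, the ratio jumps between plus and minus infinity. Ranking resampled ratios from low to high then no longer ranks them from favourable to unfavourable, and cut-offs in that ranking are not confidence limits in any useful sense.

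Cost saving is one of the hypothesised outcomes, so a negative ICER is a result the sponsor expects may occur. Net health benefit avoids both problems, but it cannot be computed without a cost-per-QALY value, and none is stated. As written, the analyst would choose both the leading measure and the threshold after seeing the data.

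**Working it through.** **Inputs.** The economic sections state no expected cost or QALY difference, no SD, no power and no threshold, so there is no plan figure to reproduce. The numbers per arm come from Sample Size Estimations: 107 evaluable and 134 enrolled. Every cost, QALY and threshold value below is an assumption, varied over a range where shown.

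**1. Sign ambiguity.** ICER = ΔC/ΔQ, and net health benefit NHB = ΔQ − ΔC/λ. Take λ = $50,000.

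- Cheaper and better (−$1,000, +0.02): ICER = −$50,000; NHB = 0.02 + 1,000/50,000 = +0.04.
- Dearer and worse (+$1,000, −0.02): ICER = −$50,000; NHB = −0.02 − 0.02 = −0.04.

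The ratio is the same, while net health benefit has opposite signs.

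**2. The threshold decides the verdict when cost and QALYs both rise.** For (+$1,000, +0.02), NHB at λ = $25,000 is 0.02 − 0.04 = −0.02. At λ = $100,000 it is 0.02 − 0.01 = +0.01.

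**3. Chance that the estimated QALY difference is at or below zero.** P = Φ(−d / (SD × √(2/n))).

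- SD 0.15, d = 0.02, n = 107: SE = 0.15 × √(2/107) = 0.0205; P = Φ(−0.975) = 16.5%.
- Same inputs, n = 134: SE = 0.0183; P = Φ(−1.09) = 13.8%.
- Over SD 0.10-0.20, d 0.01-0.03 and n 107-134: from 0.7% (SD 0.10, d 0.03, n 134) to 36% (SD 0.20, d 0.01, n 107).

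**4. What the interval looks like.** 20,000 draws of independent normal mean differences, n = 107 per arm, cost SD $10,000, QALY SD 0.15, λ = $50,000:

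| Result | Cheaper and better (−$1,000, +0.02) | Dearer and worse (+$1,000, −0.02) |
|---|---|---|
| ICER, percentile 95% CI | −$680,000 to +$619,000 | −$701,000 to +$678,000 |
| Cost CI | −$3,660 to $1,670 | −$1,688 to $3,676 |
| QALY CI | −0.020 to 0.060 | −0.060 to 0.020 |
| NHB (95% CI) | +0.040 (−0.027 to 0.106) | −0.040 (−0.106 to 0.028) |
| P(NHB > 0) | 0.88 | 0.12 |

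For the cheaper-and-better case, the ICER interval runs from −$481,000 to +$334,000 at cost SD $5,000 and QALY SD 0.10, and from about −$1.05 million to +$1.00 million at $20,000 and 0.20. With a QALY difference of +0.05 the order problem recedes: the QALY CI is 0.010 to 0.090, and under 1% of draws fall below zero. The sign ambiguity remains.

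**5. Coverage.** 400 simulated trials with 1,000 resamples each; 134 per arm, QALY SD 0.15, gain 0.02, gamma costs with mean about $20,000 and SD about $10,000, true cost difference −$500, 0 or +$500. On average 21-24% of resamples had a QALY difference at or below zero, and in about 80% of trials more than 2.5% did. Percentile ICER intervals covered 98-100%, with a median width of $1.1-1.2 million per QALY. Net health benefit at $50,000 covered about 96%. Monte Carlo error at 400 trials is about 1 percentage point (√(0.95 × 0.05/400) = 0.011).

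**The case against.** The strongest reply is that the plan already contains what is needed. The sentence that allows an ICER interval also lists net health benefit and plans separate intervals for costs and QALYs, and these distinguish the mirror-image cases in the table. The Cost Analysis section tests costs directly, so the cost-reduction part does not rest on the ratio. The plan does not specify percentile intervals, only nonparametric bootstrapping. Every economic input above is assumed, and the hypothesis is tertiary.

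Much of this stands, and it rules out several stronger readings that a reader might infer:

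- That Hypothesis 3 is judged on the ICER interval alone, or that the planned analysis cannot tell cheaper-and-better from dearer-and-worse. The other planned intervals show the quadrant.
- That the hypothesis is a prediction of cost savings only. Its second part is met by either cost saving or cost-effectiveness.
- That the ICER interval would produce a false claim of cost-effectiveness. The simulation shows over-coverage, not false precision.
- That choosing between the ICER and net health benefit can reverse the point verdict. At a fixed threshold, an ICER read with its quadrant agrees with the sign of net health benefit. What is open is the threshold and how uncertainty is expressed.

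The reply does not supply a verdict on cost-effectiveness. In the base case both separate intervals span zero and the plan gives no rule for combining them. Net health benefit is optional and cannot be computed as written. The order problem lies in ranking the ratios, so the missing detail on interval type does not remove it.

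**Conclusion.** The concern holds in a limited form. The plan permits a bootstrap CI for the ratio that Hypothesis 3 names as its measure, and that interval is not valid when resampled QALY differences straddle zero. The plan also leaves the lead measure and the threshold unset, so its second part has no fixed criterion for being cost-effective.

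The size depends on inputs that the document does not give. At QALY SD 0.15 and a gain of 0.02, zero is crossed often and the ICER interval is more than $1 million wide. At a gain of 0.05 crossing is rare. The consequence is an uninformative interval and room to choose the threshold after the fact. The SAP should be changed, but the primary and secondary clinical conclusions do not depend on it.

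**What to change.** In the Cost-Effectiveness Analysis section:

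1. Make incremental net health benefit the lead measure for each comparison (coping skills versus education, and versus usual care), with its bootstrap 95% CI, at one primary cost-per-QALY threshold and a stated range around it.
2. From the same resamples, show the cost-QALY scatter and an acceptability curve.
3. Report the ICER as a point estimate with its quadrant: cost per QALY gained when both differences are positive, savings per QALY forgone when both are negative, and dominance in words only when the signs differ. Cheaper-and-worse is a trade-off and must not be labelled dominance.
4. Do not report a bootstrap CI for the ICER when the resamples cross zero QALY difference.

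The separate cost and QALY intervals and the direct cost comparison stay as planned. The cost is SAP wording only, with no new data and no extra resampling. The one real burden is that the sponsor must name a threshold in advance.

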Testing for the presence of mediation (illustrated in Figure 1) will allow us to determine the extent to which pain catastrophizing^{28,29,39} mediates the relationship between pain coping skills training and outcome. The dashed

line between pain coping skills training and WOMAC Pain represents the hypothesized mediation (either partial or complete) of pain coping effects by pain catastrophizing. Understanding whether catastrophizing is a mediator for pain coping skills treatment response will provide a causative explanation for how pain coping skills training effectively improves outcomes following knee arthroplasty. If our study finds that pain coping skills training (CST) is effective and that pain catastrophizing explains these effects, the field of orthopaedic surgery could experience substantive changes in the way in which patients with knee arthroplasty are treated; to the benefit of many patients. Surgeons may begin to routinely screen for high pain catastrophizing and initiate pain

coping skills training for selected patients.

Innovation: Specific Aim 1

Current clinical paradigms do not discuss formal identification of patients at-risk for poor outcome due to poor pain coping.⁴⁰ Nor do these paradigms address the use of perioperative interventions to reduce poor outcome risk. The current application challenges this practice paradigm. If our trial is successful, as we anticipate it will be based on our pilot work, the research will provide strong evidence to reconsider this traditional approach and may improve outcomes for thousands of patients who currently are at-risk for poor outcome.

Previous work by our group²⁹ and others^{27,28,31,39} has identified a TKA patient subgroup at high risk for poor outcome. Patients with high levels of pain catastrophizing have been consistently shown to have a higher rate of persistent pain and compromised function compared to non-catastrophizers. Our study is innovative because it is the first trial, to our knowledge, to target a specific surgical subgroup of patients at risk for poor outcome. In addition, we completed a search of ClinicalTrials.gov and the World Health Organization registry portal on June 1, 2011 and found no trials examining the impact of pain coping skills behavioral interventions for patients with knee arthroplasty.

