effect of 2 WOMAC Pain points for coping skills training for three reasons. First, our pilot study used a quasi-experimental design which may overestimate treatment effects because of non-randomization. Second, estimates were based on comparisons to usual care, and we suspect that some therapeutic benefit will be experienced by the arthritis education group. Third, these data represent only short-term changes following surgery and most patients continue to improve up to a year following surgery.^{9,14}

Using a two-sided two group 0.05-level t-test of differences in means and assuming the intervention difference minus the arthritis education control difference is at least 2.0 WOMAC Pain points, a sample size of 107 in each group will have 91% power to detect this difference, assuming that the common standard deviation is 4.34 (based on pilot work described earlier). This corresponds to an effect size of 0.46 which is consistent with the effect of other behavioral interventions for knee arthritis.¹²⁷⁻¹²⁹ This sample size also adequately powers the study to detect a 20% difference between groups in the number of patients with a 50% or greater improvements in WOMAC pain relative to baseline scores.^{9,10,12-15,130} This effect will be equivalent to an odds ratio of 2.25 and is equivalent to a Numbers Needed to Treat (NNT) of 5 which is indicative of an effective intervention.¹³¹ The revised CONSORT statement endorses use of indexes such as number needed to treat.¹³²

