Periodic and ad-hoc reporting will be utilized to show subject recruitment and retention data stratified by site. Automated email agents will electronically notify site staff and investigators of upcoming and overdue subject follow-ups. Upon request, the data manger will provide de-identified data in a form agreeable to the biostatistician. In addition, the DMG will provide timely troubleshooting assistance via phone and email and answer inquiries from research staff and investigators. The investigators will develop a User’s Guide to aid the study staff with data management tasks should the study be funded.

Approach: Specific Aim 2

We will collect Pain Catastrophizing Scale, WOMAC Pain and Disability Scale and a verbal pain rating scale scores on all patients at six time points (4 to 6 weeks prior to surgery, 1 week prior to surgery, 1 week following surgery, 2 and 6 months following surgery and 1 year following surgery). Our rationale is that we want to capture the short- and intermediate-term temporal progression of changes in catastrophizing prior to and following treatment to describe changes in mediation over time. The primary outcome measure will be the WOMAC Pain scale, collected at all assessment points. The independent variable will be treatment condition (Pain Coping Skills Training vs Arthritis Education vs usual care). (Figure 1)

Our hypothesis is that the effects on WOMAC Pain by the pain coping skills arm will be either partially or fully mediated by pain catastrophizing, whereas effects by arthritis education or usual care will either not be mediated by pain catastrophizing or mediated to a significantly lesser extent as compared to the pain coping skills arm. Mediation will be investigated using the three-step approach described by Baron and Kenny¹⁷ and modified for randomized trials by Smeets and colleagues.¹⁴⁴ A series of 3 multilevel regression analyses will be used to determine if pain catastrophizing mediates the effect of the interventions on pain as measured with the WOMAC Pain scale at the various time points. WOMAC Disability and verbal pain rating scores will serve as secondary outcome measures for the mediation analysis.

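### Aim 2 allows a finding of partial or full mediation but sets no rule for telling them apart; if loss of significance is the rule, an effect only half mediated could often be labelled full

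*Combined protocol and SAP*

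**What the plan says.** Under Approach: Specific Aim 2, the hypothesis is that the effect of coping-skills training on WOMAC Pain "will be either partially or fully mediated by pain catastrophizing". Under Significance: Specific Aim 2, the dashed line in Figure 1 "represents the hypothesized mediation (either partial or complete) of pain coping effects by pain catastrophizing". That section also presents the analysis as a way to learn how far catastrophizing accounts for the treatment effect.

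On method, the Approach section says: "Mediation will be investigated using the three-step approach". It attributes the approach to Baron and Kenny and cites a modification for randomized trials, which it does not describe. It continues: "A series of 3 multilevel regression analyses will be used to determine if pain catastrophizing mediates the effect of the interventions on pain".

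The plan does not name the direct effect, the indirect effect or the proportion mediated as quantities to be estimated. It gives no confidence interval or bound for any of them, no criterion separating full from partial, and no power for Aim 2. Hypothesis 4 in Specific Aims says only that change in catastrophizing will mediate improvement.

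**The concern.** The plan mentions two grades of mediation and names one tool. As conventionally read, the three-step method separates the grades in its last regression. If the treatment coefficient is still significant with the mediator in the model, mediation is called partial; if it is not, mediation is called full. Full mediation is then a claim that the direct effect is zero, supported only by a failure to reject zero. The less precise the trial, the more often it would earn the stronger label.

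The label affects how the result is read. Significance: Specific Aim 2 says mediation would supply a causal explanation, and links the finding to possible routine screening by surgeons. The training also teaches activity pacing, relaxation and skills that the protocol says can help with depression, so a route that bypasses catastrophizing is plausible.

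**Working it through.** **Inputs from Sample Size Estimations.** The test is described as "Using a two-sided two group 0.05-level t-test of differences in means", the assumption is that "the intervention difference minus the arthritis education control difference is at least 2.0 WOMAC Pain points", and the calculation proceeds "assuming that the common standard deviation is 4.34". There are 107 evaluable and 134 enrolled patients per arm.

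**Assumptions not in the plan.** The 0.05 two-sided level applies to each mediation step. The rule for full is a non-significant direct effect. Half the 2-point effect is mediated, so the true direct effect is 1 point. The effect on catastrophizing, d, has no planning value. The Pilot Intervention Study gives 0.71 to 0.96 for three outcomes together, so 0.3 to 0.96 SD was tried.

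**Step 1: reproduce the plan's power.** SE = 4.34 × √(2/107) = 0.593, and 2/0.593 = 3.37. Power = Φ(3.37 − 1.96) = 92% (91.9% by noncentral t). The plan states 91%, so its figure reproduces.

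**Step 2: crude check on the direct effect.** Same SE with a 1-point effect: 1/0.593 = 1.69. P(not significant) = Φ(1.96 − 1.69) = 61%. With 134 per arm it is 53%. For 80% power to detect 1 point, n = 2 × (1.96 + 0.84)² × 4.34² = about 296 per arm.

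**Step 3: put the mediator in the model.** With d = 0.71:
- Mediator slope b = 1/0.71 = 1.41. Within-arm correlation r = 1.41/4.34 = 0.32.
- Residual SD = 4.34 × √(1 − r²) = 4.11.
- SE(direct) = 4.11 × √(2/107) × √(1 + d²/4) = 4.11 × 0.137 × 1.06 = 0.60.
- 95% CI half-width = 1.96 × 0.60 = 1.2 points, against a total effect of 2.
- P(not significant) = Φ(1.96 − 1/0.60), about 61%.

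If the effect were truly all mediated, SE(direct) is 0.48 and the half-width 0.9 points. Even then the data would usually leave open a direct effect close to half the planned benefit.

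**Step 4: simulate all steps.** Full is counted when the total effect, treatment-to-mediator and mediator-to-outcome tests are all significant and the direct effect is not. The effect is half mediated and the outcome SD is 4.34.

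| Mediator effect (SD) | Implied r | Full, 107 per arm | Full, 134 per arm |
|---|---|---|---|
| 0.3 | 0.77 | 15% | 12% |
| 0.44 | 0.52 | 42% | 38% |
| 0.5 | 0.46 | 46–47% | 43% |
| 0.71 | 0.32 | 53–55% | 48–50% |
| 0.96 | 0.24 | 56% | 55% |

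Repeat runs moved these by up to about 2 percentage points.

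**Step 5: vary the other inputs (107 per arm).**
- SD 3.76, which is 4.34 × √(1 − 0.5²), a baseline correlation of 0.5: full in about 37–52% over d = 0.5 to 0.96.
- SD 3.0, where adjustment removes 1 − (3.0/4.34)² = 52% of the variance: about 10–35% over the same range.
- Total effect 4.2 points, as in the pilot: 0–4% over the same range.
- 75% mediated, d = 0.71, SD 4.34: about 78%.

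**The case against.** The strongest objection is that the criticised rule is not in the documents. No section says a non-significant direct effect will be reported as full mediation, and the cited modification for randomized trials may change the last step. This stands. A reader might infer that the plan commits to that rule; the text does not support it. What the text shows is a distinction drawn twice with no stated way to make it.

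Second, partial-or-full is wording within a hypothesis that either result satisfies. The regressions are there to decide whether catastrophizing mediates. The link to screening in Significance: Specific Aim 2 depends on the training working and catastrophizing explaining its effect, and it does not require full mediation. This also stands. It limits the point to how strongly the mediation result is worded.

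Third, the base inputs are mixed. The 2-point effect was deliberately cut from the pilot's 4.2, while 0.71 SD is an uncut pilot figure. Shrinking it in proportion gives 0.46/0.74 × 0.71 = 0.44 SD, and full in 42% (107 per arm) or 38% (134). The planned models are also multilevel, with three arms and six time points, and the Data Analysis section has baseline covariates in the primary model. The check uses two arms at one time point. Adjustment could lower the residual SD and hence the rate. So a reader might take mislabelling in about half of trials as a fixed property of the design, and that goes too far.

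What survives is that, at the plan's own sample size, SD and effect, the direct effect is estimated too imprecisely for its non-significance to mean that it is absent.

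**Conclusion.** The point holds as a gap in how the mediation result will be interpreted. Aim 2 contemplates full mediation without saying what would establish it. The conventional reading of the named method would let absence of significance stand for absence of a direct effect.

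Under that reading, with 107 per arm, SD 4.34, a true total effect of 2 points and a mediator effect of 0.5 to 0.96 SD, a half-mediated effect would be labelled full in about 46 to 56% of trials. The figure is conditional. It falls to about 40% at 0.44 SD, 15% at 0.3 SD, 37–52% at SD 3.76 and 10–35% at SD 3.0, and to near zero for a pilot-sized total effect.

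The documents do not support saying that the plan has adopted this rule, or that the error undermines the trial's main result. The primary analysis, and the question of whether there is any mediation, are untouched.

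**What to change.** In Approach: Specific Aim 2:
- Report three quantities side by side, each with a 95% CI: the total effect, the direct effect (the treatment coefficient with catastrophizing in the model) and the indirect effect (for example with a bootstrap interval).
- State that a non-significant direct effect will not be read as full or complete mediation.
- Describe the extent of mediation from these estimates and their intervals. Align the wording about partial or complete mediation in Significance: Specific Aim 2.
- Say in a sentence what the cited modification for randomized trials changes in the three steps.

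No equivalence margin is required. The cost is a few lines of text: the direct effect and its interval come from the third regression already planned, and the indirect effect needs only a bootstrap of the same models. The downside is that the trial will seldom be able to claim full mediation, because at this size the direct effect is known only to within about 0.9 to 1.2 points.
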